By connecting this device to a manometer, its performance can be tested during the VM strain. As there is a normal physiological response to the VM which varies according to the degree of vagal tone, the effects of a VM using the device can also be compared to a strain using a manometer alone and with and without postural modification by assessing the fall in pulse rate during the manoeuvre.⁶

Demonstrating the device is as effective as a manometer and works with a posture modified VM in normal volunteers would support its use in routine care and enable further evaluation in patients. The device, packaged with instructions for use, would be a useful piece of equipment for use in emergency departments and by paramedics and for patients who suffer from SVT.

Aims and objectives

Aims:

- The aim of this study is to confirm the physiological effects of a modified VM and evaluate the performance of a novel Valsalva assist device in healthy volunteers

Objectives:

- To evaluate whether there is a difference in vagal tone (drop in heart rate) in healthy volunteers performing a modified VM verses a standard supine VM using the VAD.
- To evaluate whether there is a difference in vagal tone (drop in heart rate) in healthy volunteers performing a modified VM verses a standard supine VM using a manometer.
- To measure and compare peak strain pressure and duration produced using the device compared to a standard manometer in supine and modified postures

Figure 1. Valsalva Assist Device (VAD). Fitted with disposable mouth piece and filter

Research Design

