The VM is an extremely safe, physiological manoeuvre which is used in everyday life (eg straining at stool) and has been used in trial conditions and clinical practice many thousands of times with no serious adverse events. We will exclude participants who could conceivably be at any risk of harm from performing a VM or from use of the device.

Screening will include 12 lead ECG and physical examination including observations of pulse, oxygen saturations, respiratory rate and blood pressure. Any participants with any detected abnormalities whether they are excluded from participation or not will be informed and referred to their primary care physician as appropriate. All testing will be conducted in the clinical research facility (CRF) of the Royal Devon & Exeter Hospital, according to a strict trial protocol.

Figure 2. Inclusion and Exclusion Criteria

Inclusion Criteria:

Adult Volunteers between 18 and 60 years old from University of Exeter or RD&E Hospital staff

Sinus rhythm on initial ECG

Self-reported good health

Exclusion Criteria:

Any regular medication other than the oral contraceptive

Previous cardiovascular or respiratory disease

Any contra-indication to performing a VM strain. (Eg. Known aortic stenosis, recent myocardial infarction, glaucoma, retinopathy)

Pregnancy

Any ECG abnormality

Any contra-indication to postural modification (any reason the participant can't lie flat and have both legs lifted to 45 degrees, eg prosthetic hip)

Inability or refusal to give written consent to take part

Observations of pulse, oxygen saturations, respiratory rate or blood pressure outside the normal range. Specifically blood pressure less than 100 systolic

Caffeinated drinks within 6 hours prior to testing

The use of stimulant drugs or alcohol within 24 hours prior to testing

Test Valsalva Manoeuvres:

Participants will undergo a total of 4 VMs of the following 4 variations in random order, stratified by method of strain generation to ensure balance between the order of manometer and device use:

1. *Supine VM using manometer.* Supine Valsalva strain using a manometer visible to the participant with a target of 40mmHg for 15 seconds
2. *Supine VM using device.* Supine Valsalva strain using the device connected to manometer invisible to the participant but visible to a researcher for 15 seconds

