There will be a three minute washout period between strains including two minutes rest after any change in posture. Continuous 3 lead ECG monitoring on a standard print enabled monitor will be used to assess heart rate during the manoeuvre. ECG rhythm strip traces would be printed for 45 seconds (15 seconds before, during and 15 seconds after each VM). They will be marked at the onset of each Valsalva strain, labelled with a code and subsequently analysed, blind to technique according to the method described by G Smith⁶:

Pre-manoevr heart rates will be determined by calculating the mean R-R interval of the 10 beats preceding each manoeuvre before converting it to heart rate in beats/minute. The lowest post manoeuvre heart rate will be determined by measuring and recording the longest R-R interval during and up to 15 seconds post manoeuvre. This will also be converted to a heart rate in beats per minute. The difference between the pre and post manoeuvre heart rate will indicate the degree of vagal tone or slowing of heart rate induced by each manoeuvre.

Peak sustained pressures achieved as observed on the manometer and duration of longest strain attempt during all VMs will be recorded on a standard report card. This will allow comparison of the different strain techniques.

Participants will be closely monitored for any adverse events. Though none are expected, if any participant feels unwell or develops any significant or persistent ECG abnormalities, the individual will be immediately withdrawn from further testing and appropriate further clinical assessment will be arranged. All adverse events will be recorded, graded and reported immediately to the CI and sponsor and reviewed by the study team.

Data Management

The data will be de-identified and stored on encrypted and password protected computers and laptops. Personal data such as name and e-mail address will be held separately. All data will be stored on University of Exeter computers with a designated University of Exeter member of staff responsible for destruction. Paper copies need to be scanned and destroyed and electronic records kept for a period of 5 years following the completion of the study, in line with University guidelines. The member of staff responsible for data storage and disposal will be the Chief Investigator ([name]) or their designated deputy from the research team at the University of Exeter.

Software

Data will be stored on Excel and analysed using STATA.

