Statistical Analysis (Revised)

The heart rates measured under each of the four testing scenarios will be summarised appropriately, e.g. mean and SD, or median and IQR if necessary; it is expected that heart rate will be approximately normally distributed.

The contrasts of interest are to compare heart rate for:

1. Supine VM vs modified VM (recognising that this comparison may or may not be different according to which instrument is used – manometer or device)
2. Manometer vs device (recognising that this comparison may or may not be different according to the posture adopted – supine or modified)

The analysis will be based on mixed effects linear regression (with appropriate prior assessment of assumptions, e.g. Normality), with individual as a random effect, position (supine/modified) as a fixed effect and instrument (manometer/device) as a fixed effect. An interaction term (position x instrument) will be examined to consider whether there is any evidence of a differential effect (of device according to position, or equivalently position according to device), but will be dropped from the model if $p > 0.1$. If the interaction term is retained then comparison 1 between postures will be presented separately by device, and comparison 2 between devices will be presented separately by posture type; otherwise the two comparisons will be presented overall.

Sample size calculations are based on a simple paired t-test. There is no obvious way to determine a “smallest clinically important difference”, but we have used 4 beats per minute as a reasonably small difference, below which is unlikely to be important clinically. The SD reported in G Smith et al is about 12 (similar for individual measures and for differences between measures). With these parameters, a sample size of at least 73 participants provides 80% power at the 5% level of significance.

Project management

The programme team consists of a multidisciplinary team with complementary skills and expertise as follows:

[name] is the Chief Investigator and will lead the project and provide clinical expertise and advice.

[name] is a statistician and director of the research design service. He will advise on design and statistical aspects of the project.

[name] will run the day to day practical aspects of the study as part of her Intercalated Master by Research Project

[name] will act as academic supervisor and provide academic support to the project.

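### The mixed model has no term for the pre-manoeuvre rate measured before each strain, so the device-versus-manometer interval may be somewhat wider than it need be (efficiency only; optional, minor)

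*Combined protocol and SAP*

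**What the plan says.** All references are to the combined protocol and SAP.

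- **Measurement (Test Valsalva Manoeuvres, ECG method).** Each strain has its own baseline: "Pre-manoevr heart rates will be determined by calculating the mean R-R interval of the 10 beats preceding each manoeuvre". The longest R-R interval gives the lowest rate, and "The difference between the pre and post manoeuvre heart rate will indicate the degree of vagal tone or slowing of heart rate induced by each" strain.
- **Aims and objectives.** The first two objectives, which compare postures, use the same quantity: "To evaluate whether there is a difference in vagal tone (drop in heart rate) in healthy volunteers".
- **Statistical Analysis (Revised).** The outcome is worded more loosely: "The contrasts of interest are to compare heart rate for" supine against modified (contrast 1) and manometer against device (contrast 2). The model is "with individual as a random effect, position (supine/modified) as a fixed effect and instrument (manometer/device) as a fixed effect", with a position-by-instrument interaction that is dropped if p > 0.1. No pre-strain rate is listed.
- **Design.** The four strains are performed "in random order, stratified by method of strain generation to ensure balance between the order of manometer and device use". Between strains, "There will be a three minute washout period between strains including two minutes rest after any change in posture".

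**The concern.** A random intercept removes a person's stable level. It does not remove variation in resting rate from one strain to the next. Suppose a volunteer's rate happens to be higher before the device strain than before the manometer strain. The drop then absorbs whatever part of that difference the lowest rate does not follow. If the lowest rate itself is analysed, it absorbs the part that does carry through. Either way, noise that the trial has already measured can stay in contrast 2.

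Adjustment is legitimate for this contrast. Order is randomised with balance by instrument, both strains in a given posture start from the same position, and the 10 beats precede the strain. The background section hopes to show that the device works as well as a manometer, and the width of this interval bears on that.

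**Working it through.** **1. The plan's own figure.** Inputs from Statistical Analysis (Revised): difference 4, SD 12, 80% power, 5% level, paired t-test. The normal approximation gives (2.8016 × 12/4)² = 8.405² ≈ 70.6, so 71. The two-sided noncentral-t calculation gives 73, with power 80.2%. The stated 73 reproduces.

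**2. Planned precision of contrast 2.** The plan gives an SD of about 12 both for single measures and for differences. It does not say which differences, so applying this to the drop is an assumption. It implies a within-person residual variance of 12²/2 = 72.

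- With no interaction, contrast 2 averages two device-manometer differences per person, with variance 144/2 = 72.
- SE = √(72/73) = 0.993; 95% half-width = 1.96 × 0.993 ≈ 1.95 beats/min.
- For a 4-beat difference, 4/0.993 − 1.96 = 2.07, a power of about 98%.

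**3. Gain if the drop is analysed.** Two quantities are not in the documents and are assumed: *s*, the within-person SD of the pre-strain rate, and *L*, the share of a pre-strain deviation that carries through to the lowest rate. A deviation u enters the drop as (1 − L)u, so adjustment removes (1 − L)²s²/72 of the variance:

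| L | s = 2 | s = 4 | s = 6 |
|---|---|---|---|
| 0 | 4/72 = 5.6% | 16/72 = 22.2% | 36/72 = 50% |
| 0.3 | 1.96/72 = 2.7% | 7.84/72 = 10.9% | 17.64/72 = 24.5% |
| 0.5 | 1/72 = 1.4% | 4/72 = 5.6% | 9/72 = 12.5% |
| 0.7 | 0.36/72 = 0.5% | 1.44/72 = 2.0% | 3.24/72 = 4.5% |
| 1 | 0 | 0 | 0 |

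On the scale of the interval, at L = 0.3, 1.96 × √((72 − 0.49s²)/73) falls from 1.947 to 1.920, 1.837 and 1.691 for s = 2, 4 and 6. Simulation with 73 participants (4000 runs) gave SEs falling from 0.995 to 0.982, 0.978 to 0.930 and 1.000 to 0.875. Multiplied by 1.96, these are reductions of 0.03, 0.09 and 0.25 beats/min. Coverage was 94.9 to 95.1%.

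**4. Gain if the lowest rate is analysed.** The share becomes L²s²/72, taking 72 as that outcome's residual variance. At L = 0.3 it is 0.5%, 2.0% and 4.5% for s = 2, 4 and 6. At L = 1 and s = 4 it is 22.2%. The dependence on L is reversed.

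**5. A more favourable parameterisation.** Suppose the pre-strain and lowest rates have equal within-person variances and correlation r. Adjusting the drop then multiplies the SD by √((1 + r)/2): the interval is 19%, 13%, 8% and 3% narrower at r = 0.3, 0.5, 0.7 and 0.9. But a drop variance of 72 = 2(1 − r)s² then requires s = √72 ≈ 8.5 at r = 0.5, above the range in step 3.

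**6. Effect on contrast 1.** A pre-rate centred within participant and posture sums to zero in each such pair, so with complete data the overall posture estimate does not move. An uncentred pre-rate does move it: with an assumed 3-beat resting difference between postures and L = 0.3, a posture effect of 4.0 becomes 4.0 − 0.7 × 3 = 1.9.

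**7. Effect on reported intervals.** The centred covariate lowers the error of the instrument and interaction comparisons but not of the posture comparison, while the random-intercept model pools all three. At s = 6, L = 0.3 the pooled variance is (72 + 2 × 54.36)/3 = 60.24. The posture SE would then be reported at √(60.24/72) = 0.91 of its true size. Contrast 2's reported half-width would be 1.96 × √(60.24/73) = 1.78 rather than 1.69.

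**The case against.** The strongest reply is that nothing here is wrong. The drop is a valid outcome that already uses the pre-strain rate, and the plan works to keep the baseline steady through five minutes' initial rest, the washout and a 10-beat mean. On the plan's own SDs, contrast 2 already has about 98% power for 4 beats/min, and the gain at L = 0.3 is at most about a quarter of a beat. Quoting variance percentages makes that look larger than it is. The only listed objective that compares device with manometer concerns strain pressure and duration, so contrast 2 rests on the second research question and the analysis section. Participants also know which instrument comes next, so anticipation could affect the 10 preceding beats.

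Most of this stands, and it makes the point optional. It does not remove the point: the covariate is already collected, and when there is nothing to gain the simulated SE rose by at most 0.4%. Anticipation is a possibility that the documents neither show nor exclude.

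A reader might infer that the plan ignores the baseline altogether. The documents do not support that, because the objectives and the ECG method define the effect as the drop. It would be literally true only if *heart rate* in the analysis section meant the lowest rate.

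**Conclusion.** The point holds as a minor, optional gain in efficiency. No term adjusts for the strain-specific baseline, so chance within-person baseline variation can widen the contrast 2 interval under either reading of the outcome.

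For the drop, the variance reduction at s = 4 runs from 22% (L = 0) to nil (L = 1). At L = 0.3 and s = 2 to 6, the half-width of about 1.95 beats/min narrows by about 0.03 to 0.25. These figures rest on assumed s and L and on a residual variance of 72 inferred from the plan's remark about SDs.

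It would be wrong to go further and conclude that contrast 2 is biased or that 73 is too few. Randomised order makes instrument differences in the baseline a matter of chance, apart from possible anticipation, and 73 follows from its own inputs. Nor do the documents show that the planned interval is too wide for its purpose.

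**What to change.** In Statistical Analysis (Revised):

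1. Name the drop (pre-strain rate minus lowest rate) as the outcome.
2. Add one covariate to the mixed model: the pre-strain rate minus that participant's mean pre-strain rate in the same posture.
3. Report contrast 2 from this model, and take the single position-by-instrument test (the existing p > 0.1 rule) from it, so that one result governs how both contrasts are presented.
4. Do not use an uncentred pre-rate for contrast 1, because starting posture differs between supine and modified strains. The overall contrast 1 estimate is unchanged with complete data; take its interval from the fit without the covariate, for the reason in step 7 of the working. A participant-by-posture random intercept in the adjusted model would be an alternative, and would also let contrast 2's reported interval show the full gain.
5. Show the unadjusted contrast 2 as a sensitivity analysis. This is the same fit as in item 4.

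The cost is a few sentences in the SAP, one extra parameter and one extra fit, with no new data. The gain may be small, and the adjusted result assumes that anticipating the instrument does not alter the 10 preceding beats.

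### The objectives ask for the posture effect with the VAD and with the manometer separately, but the analysis gives a separate contrast for each only if the interaction has p ≤ 0.1

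*Combined protocol and SAP*

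**What the plan says.** Under Aims and objectives, two objectives are tied to an instrument. One concerns volunteers "performing a modified VM verses a standard supine VM using the VAD"; the other concerns volunteers "performing a modified VM verses a standard supine VM using a manometer". The first research question, by contrast, asks about posture without naming an instrument.

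Statistical Analysis (Revised) fits a mixed linear model with a random effect for individual and fixed effects for position and instrument. It tests the interaction and removes it if p > 0.1. What is then shown depends on that test: "If the interaction term is retained then comparison 1 between postures will be presented separately by device"; "otherwise the two comparisons will be presented overall".

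One instrument-specific output is planned in every case: "The heart rates measured under each of the four testing scenarios will be summarised appropriately", as mean and SD or median and IQR. The section does not mention a confidence interval on either branch.

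The design supplies the data for both contrasts: "Participants will undergo a total of 4 VMs of the following 4 variations in random order". On sample size: "Sample size calculations are based on a simple paired t-test", with a difference of 4 bpm, SD about 12 and at least 73 participants for 80% power.

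**The concern.** A data-dependent preliminary test decides whether two stated objectives receive an estimate of their own. If the two instruments behave alike, the term will usually be dropped, and the report will then contain one posture effect averaged over VAD and manometer.

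The scenario summaries do not fill the gap. Subtracting two scenario means gives a crude posture difference for one instrument, provided the data are complete and means rather than medians are shown. The separate SDs do not give the standard error of a within-person difference, which is what a repeated-measures design is meant to exploit.

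At stake is the evidence on the VAD, the new product. Half the information in the overall effect comes from the manometer. It answers the VAD objective only if the posture effects are the same with both instruments, and a non-significant interaction test does not establish that.

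**Working it through.** **Inputs from Statistical Analysis (Revised).** n = 73; difference 4 bpm; SD of differences 12; 5% level; 80% power; interaction dropped if p > 0.1.

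**Assumptions.** Complete data. The VAD and manometer posture differences each have SD 12. Their correlation r is not given, so r = 0, 0.3 and 0.5 are shown.

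**1. The plan's own sample size.** For a paired t-test the noncentrality is 4/(12/√73) = 4/1.404 = 2.85 on 72 df. Two-sided 5% power is 80.2% at n = 73 and 79.7% at n = 72, so 73 reproduces. This is also the power of one instrument-specific posture contrast.

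**2. Standard errors at r = 0.** Residual variance is 144/2 = 72, with 216 df.
- One instrument: 12/√73 = 1.40 bpm; 95% half-width about 2.8.
- Overall posture effect: 12/√(2×73) = 0.99 bpm; half-width about 2.0.
- Interaction: √(4×72/73) = 1.99 bpm; half-width about 3.9.

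**3. Chance that the term is dropped at r = 0** (noncentral t, p > 0.1).

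| True interaction (bpm) | Dropped |
|---|---|
| 0 | 90% |
| 3 | 55% |
| 4 | 36% |
| 6 | 9% |

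**4. The same at 4 bpm with correlation.** The within-person variance is 72(1+r) for the position contrast and 72(1−r) for the interaction. With a standard error specific to each contrast, the term is dropped in 22.9% of trials at r = 0.3 and 11.9% at r = 0.5. A random-intercept model pools the contrast variances, so the result also depends on the instrument contrast, varied here from 72(1−r) to 72(1+r). This gives 29.8–36.9% at r = 0.3 and 23.7–37.2% at r = 0.5. The full range is 12–37%.

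**5. What the reported interval says about the VAD** (simulation of the rule).
- No interaction, r = 0: the interval covers the VAD effect about 93% of the time, against 95% if the contrast is always separate.
- VAD effect 0, manometer effect 4 bpm, r = 0: coverage of the VAD effect is about 79% over all trials and about 48% among trials where the term is dropped. With r = 0.3–0.5, coverage over all trials is 80–92%.
- In the same case at r = 0, the overall interval still covers the average of the two effects about 95% of the time when the term is dropped.
- In the same case, the term is dropped and the overall effect is significant in about 18% of trials at r = 0, and in 4–18% at r = 0.3–0.5.
- Requiring the overall estimate also to reach 4 bpm leaves 0.8% at r = 0, and at most about 2% with correlation.

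**The case against.** The plan does not overlook the issue. Its list of contrasts says openly that the posture effect may differ by instrument. The rule is fixed in advance and the 0.1 threshold is lenient. If there is truly no interaction, the additive model's posture coefficient is a fair estimate for both instruments and more precise than separate ones. The overall effect also answers the first research question directly. Nothing in the documents suggests an interaction as large as 4 bpm: both instruments aim at 40 mmHg for 15 seconds with the same posture steps. All of this stands, and it limits the size of the problem. It does not give the first two objectives an estimate of their own.

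A reader might infer more than the documents support:
- *That nothing on each instrument is reported when the term is dropped.* The four scenario summaries always are.
- *That the overall effect is invalid.* It remains valid for the average of the two instruments, and misleads only if read as the VAD answer.
- *That the trial is likely to claim a clinically relevant VAD effect that does not exist.* The plan regards 4 bpm as a difference "below which is unlikely to be important clinically", and the 0.8% to about 2% found above is small.
- *That the sample is too small for separate contrasts.* The paired t-test calculation already gives about 80% power for each one.
- *That the overall posture effect or manometer versus device should become secondary.* Both are contrasts of interest in the plan, and this point gives no reason to rank them lower.

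**Conclusion.** The mismatch is real: two instrument-specific objectives get a separate model-based contrast only when an interaction test gives p ≤ 0.1. The practical harm is modest. The probabilities rest on n = 73, SD 12 for each posture difference, complete data and, for the headline figures, uncorrelated posture differences; the correlated ranges use values the documents do not give. The textual mismatch depends on none of these assumptions. The change is worth making because it costs almost nothing and lets each stated objective be answered directly.

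**What to change.** Keep the interaction test, but do not let it decide whether the first two objectives are reported. Possible wording:

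> Whatever the p-value of the position-by-instrument interaction, we will report, with 95% CIs, modified minus supine with the VAD (objective 1) and modified minus supine with the manometer (objective 2), estimated from within-person paired differences or from the model including the interaction. The interaction estimate and the overall posture and manometer-versus-device comparisons will also be reported, with their present status.

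Paired differences are the safer choice of the two: at a correlation of 0.5, an instrument-specific 95% interval from the random-intercept model covers about 93–97%.

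Costs:
- Only the analysis wording changes; no new data or participants are needed.
- Instrument-specific half-widths are about 2.8 bpm, against about 2.0 overall if uncorrelated. At a correlation of 0.5 the overall figure is about 2.4 with a contrast-specific SE, or 1.8–2.1 with random-intercept SEs.
- For a common 4 bpm effect (uncorrelated), power is about 80% for each contrast and about 65% for both, against about 98% overall.
- If both contrasts are tested at 5% and there is no posture effect, the chance of at least one false positive is about 9–10% with paired SEs, or about 6–13% with random-intercept SEs at correlation up to 0.5. Under the current rule it is about 9.5% if uncorrelated.
- More contrasts are always shown, so the plan should state which of them are tested.
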